Encouraging Mail Order Pharmacy Use to Improve Outcomes and Reduce Disparities

NCT02621476

Document date: 10/1/2020

Encouraging Mail Order Pharmacy Use to Improve Outcomes and Reduce Disparities

CLINICAL TRIAL PROTOCOL

Abbreviations:

CVD: cardiovascular disease

HPHC: Harvard Pilgrim Health Care Institute

IVR: automated telephone call (interactive voice response)

KP: Kaiser Permanente

KPNC: Kaiser Permanente Northern California

KPHI: Kaiser Permanente Center for Health Research, Hawaii

LDL: Low-density lipoprotein

PDC: Proportion of Days Covered

OBJECTIVE:

In this study, we seek to determine whether targeted, patient-centered interventions to encourage mail order pharmacy use will result in greater rates of mail order pharmacy use as well as improvements in medication adherence. We conducted a randomized encouragement trial to encourage use of the existing mail order pharmacy among diabetes patients with poor adherence to CVD risk factor medications who use only retail pharmacies and examined whether the intervention's impact differs across key subgroups. The specific aims of this clinical trial are to:

Aim 1: To test whether outreach strategies to encourage mail order pharmacy use will increase rates of mail order pharmacy use (Primary Outcome) in diabetes patients at high risk for poor health outcomes.

Aim 2: To examine whether encouraging the use of mail order pharmacy services to deliver cardiometabolic medications results in greater medication adherence, and to assess differences in the impact of the intervention across key subgroups.

BACKGROUND:

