There is an urgent need for effective, sustainable interventions to improve diabetes medication adherence. Good medication adherence is associated with improved control of CVD risk factors, fewer hospitalizations, and lower mortality in patients with diabetes mellitus. However, only about 50-70% of patients with chronic conditions such as diabetes are adherent to their regular medications. In response to this problem, literally hundreds of interventions to improve adherence have been evaluated and published over the last 60 years. Traditional interventions almost always require substantial investments of personnel, time, and/or financial resources. However, they generally show only modest improvements in adherence, which dissipate completely once the active intervention phase concludes. Recent approaches such as medication therapy management are expensive to implement and limited to small subgroups of patients (e.g., Medicare Part D enrollees with multiple chronic diseases and multiple medications). These types of resource-intensive interventions will be challenging to disseminate and implement more widely and are unlikely to reach large numbers of adults with diabetes. Disparities in medication adherence are prevalent among patients with diabetes. The underlying reasons for these disparities in adherence are multifactorial, and include inability to afford prescribed medications, low health literacy and low health numeracy, low patient self-efficacy, inadequate patient-provider communication, and difficulty accessing pharmacies. Since poor medication adherence is linked to poor diabetes outcomes, improving adherence among minority and low-SES patients is critical in any effort to improve health care outcomes for these populations. There is only limited evidence that broadly targeted quality improvement efforts such as diabetes registries and care reminders impact disparities in diabetes care.

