This study conducted a randomized encouragement trial to encourage use of the existing mail order pharmacy among diabetes patients with poor adherence to CVD risk factor medications who use only retail pharmacies. Subjects were randomized to (2) arms: 1) the intervention arm and 2) the usual care arm. Those randomized to the intervention arm, at all sites, received encouragement to use mail order pharmacy services by receiving an outreach letter, which includes information about the benefits of mail order pharmacy use, and information on how to enroll in mail order pharmacy services at their individual site. In addition, those randomized to the encouragement at KPNC and KPHI received an encouragement outreach email (secure message) and a pre-recorded phone message. Since phone and email contact with patients is not standard of care with HPHC, they received letter-only encouragement outreach. There was no outreach follow-up. Observational EHR data was used to examine the impact of the intervention on mail order use and medication adherence. Those patients randomized to the usual care arm did not receive any form of encouragement outreach from the study team.

STUDY POPULATION:

a. NUMBER OF SUBJECTS

63,012 total participants

b. INCLUSION AND EXCLUSION CRITERIA

Inclusion Criteria:

- Age 18 years or older
- Have a diagnosis of diabetes as indicated by EHR
- Have active health plan membership in the past 12 months
- Non-adherent (PDC <80%) to at least one oral CVD risk factor medications in the past 12 months
- Have no evidence of mail order pharmacy use to refill oral CVD risk factor medications.

Exclusion Criteria:

- Pregnancy or Dementia/Traumatic Brain Injury diagnosis in the past 12 months
- Hospitalized, in Skilled Nursing Facility, Hospice, or Home Health at the time of randomization

WAIVER OF INFORMED CONSENT and HIPPA PRIVACY RULE AUTHORIZATION:

A waiver of informed consent and HIPPA Privacy Rule Authorization was granted from KPNC IRB (IRB of record for this study) for participants in the study intervention. The only known risk is disclosure of confidential information. Safeguards were be put in place to prevent the loss of privacy and to prevent breaches of confidentiality. This study represented no more than minimal risk participants.

STUDY PROCEDURES:

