To examine the relationship of encouraging MOP use with MOP use and adherence, we estimated the differences in MOP use and CVD medication adherence at follow-up between the two arms using Chi-square tests in an intent-to-treat (ITT) analysis. Differences in the percentages of CVD drug fills delivered by mail were estimated using T-Test. To determine whether MOP use differed by race/ethnicity we calculated risk ratios using modified Poisson regression comparing the effect of treatment on outcomes within each group. We used Chi-square tests to compare the percent of patients with a hospitalization or emergency department visit during follow-up between the intervention and control arm and compared the number of primary care visits between arms using the Kruskal-Wallis test. Patients who died or who disenrolled from their health plan during follow-up were excluded from the analysis. In addition, those who did not have a CVD medication fill during the follow-up period were also excluded since we were unable to assess whether they used MOP. Sensitivity analysis was conducted to assess the impact of those without CVD medication fills during follow-up by including them in the analytic population as non-users of MOP at follow-up. All analyses were further stratified by site and results from both the KP sites were collapsed based on the similarity of study results in the two sites, and because their pharmacy distribution structure and health care systems were also similar in comparison to HPHC.

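### The objective and Aim 2 ask whether the effect varies between patient subgroups, but the only patient-subgroup analysis described gives a treatment risk ratio inside each race/ethnicity group, with no comparison between groups

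*Combined protocol and SAP*

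**What the plan says.** The combined protocol and SAP raises the question twice. The Objective section says the trial examined whether the intervention's "impact differs across key subgroups". Aim 2 is to examine whether encouragement "results in greater medication adherence, and to assess differences in the impact of the intervention across key subgroups". The subgroups meant are not defined anywhere.

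The Data Analysis section is the whole of the analysis plan. For the overall comparison, "we estimated the differences in MOP use and CVD medication adherence at follow-up between the two arms using Chi-square tests". For race/ethnicity, the sentence opens with a purpose, "To determine whether MOP use differed by race/ethnicity", and continues with the method: "we calculated risk ratios using modified Poisson regression comparing the effect of treatment on outcomes within each group". Site is the only other axis: "All analyses were further stratified by site", with the two Kaiser Permanente (KP) sites then combined and set against Harvard Pilgrim (HPHC).

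**The concern.** Whether an effect differs between groups is a question about a contrast: the effect in one group relative to the effect in another, with its uncertainty. A set of group-specific risk ratios supplies the parts of that contrast but is not the contrast. Two groups can have different point estimates, or fall on opposite sides of a significance threshold, while the data remain compatible with one common effect. Equally, a set of similar-looking ratios does not show that effects are alike unless the ratio between them is estimated with useful precision.

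What is at stake is the differential-effect part of the objective and of Aim 2, and any statement about disparities, which the study title anticipates. For a disparity statement there is a second gap. Risk ratios are relative measures and do not show whether the absolute difference in use or adherence between groups became smaller.

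**Working it through.** The document states no figure on this point, so the main check is textual. The arithmetic after it is illustrative.

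**1. Question against analysis**

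| Question asked | Analysis described | Contrast between patient groups? |
|---|---|---|
| Aim 1: does outreach raise MOP use? | Chi-square test between arms | Not needed |
| Aim 2, first part: does it raise adherence? | Chi-square test between arms | Not needed |
| Objective and Aim 2, second part: does the effect vary by subgroup? | Modified Poisson risk ratio for treatment inside each race/ethnicity group | None described |
| Site | Stratified results, KP sites combined | Not a patient characteristic |

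In the race/ethnicity sentence, the thing compared is treatment, and the comparison is made inside each group. No interaction term, ratio of risk ratios, heterogeneity test or risk difference by race/ethnicity is named. The third row is therefore a question without a described estimate.

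Site stratification does not fill the gap. The outreach package differed by health system (at HPHC, "they received letter-only encouragement outreach"), so a KP versus HPHC difference cannot be separated from the package delivered.

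**2. Relative and absolute gaps can move in opposite directions**

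All inputs are assumed. Usual-care use is 10% in group A and 5% in group B. The risk ratios are 1.3 in A and 1.5 in B.

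- Usual care: ratio 10/5 = 2.00; gap 10 − 5 = 5.0 points.
- Intervention: A = 10 × 1.3 = 13.0%; B = 5 × 1.5 = 7.5%.
- Intervention: ratio 13.0/7.5 = 1.73; gap 13.0 − 7.5 = 5.5 points.

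The relative gap narrows and the absolute gap widens. The risk ratios alone would suggest only the first.

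**3. Precision of the missing contrast**

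From the document: 63,012 participants in total (Study Population). Assumed: 1:1 allocation, true risk ratio 1.2 in every group, the group shares shown, and no loss to the analysis exclusions. With n the group size, p0 the usual-care risk and p1 = 1.2 × p0:

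- SE(log RR) = √[(1−p0)/(p0·n/2) + (1−p1)/(p1·n/2)]
- The 95% limits for a ratio of risk ratios are the estimate divided and multiplied by exp(1.96 × √(SE_a² + SE_b²)).

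For groups of 5% and 40% with p0 = 10%, participants per arm are 63,012 × 0.05/2 = 1,575 and 63,012 × 0.40/2 = 12,602. The bracket (1−p0)/p0 + (1−p1)/p1 is 9 + 7.333 = 16.333. This gives SE_a = √(16.333/1,575) = 0.102, SE_b = √(16.333/12,602) = 0.036, combined 0.108, and a factor of exp(1.96 × 0.108) = 1.24.

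| Groups compared | p0 = 10% | p0 = 2% |
|---|---|---|
| 5% v 40% of participants | 1.24 | 1.64 |
| 20% v 50% of participants | 1.13 | 1.32 |

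If group shares and rates were like these, the contrast could be estimated usefully for larger groups and would be loose for a small group at low uptake. The exclusions for death, disenrolment and absence of a fill would widen every interval.

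**The case against.** The strongest reply is that this is a gap in description and not a shown error. The Data Analysis section is a single past-tense paragraph that sets out no model in full. Its race/ethnicity sentence opens with a purpose that concerns differences between groups and then names a regression. Group-specific risk ratios taken from one model with an interaction term would be described in much the same words. Race/ethnicity groups are also disjoint, so if the ratios are published with confidence intervals, a reader can form an approximate ratio of risk ratios unaided. All of this stands. It limits the point to what is described, but it does not make the described analysis answer the aim. A reader's pairwise reconstruction is also no joint test, and it cannot recover absolute gaps without the group risks.

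A reader might infer three stronger things that the documents do not support:

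- **That groups were compared by whether each result reached significance.** No such rule is stated, and the document does not show how the ratios were interpreted. Any figure for how often such a rule misleads would rest on invented group sizes, rates and effects.
- **That a promised analysis by socioeconomic status is missing.** The Background says "improving adherence among minority and low-SES patients is critical", but that is motivation. No text designates low socioeconomic status as a key subgroup.
- **That adherence was left out of the race/ethnicity analysis.** The stated purpose names only MOP use, but the method clause refers to outcomes in the plural and may include adherence.

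**Conclusion.** The point holds as a mismatch between a stated question and the analysis described for it, and it should be fixed. That no between-group contrast is described can be said with high confidence. That none was fitted cannot be said. The overall Aim 1 comparison and the overall adherence comparison do not depend on it.

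The effect on conclusions cannot be fixed from the document, which gives no allocation ratio, group sizes, usual-care rates or effect sizes. The illustrative figures show only that relative and absolute gaps can diverge and that the contrast may be imprecise in small groups. They are not evidence of what happened in this trial.

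**What to change.** For MOP use and for adherence (as the categorical measure that the Chi-square test implies):

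- Add an arm-by-race/ethnicity term to the modified Poisson model, with robust variance and adjustment for site.
- Report the joint interaction test and the ratios of risk ratios with 95% confidence intervals.
- Show these beside the planned KP and HPHC stratified results.
- Base any claim that effects differ, or are alike, across groups on these estimates and not on the separate group results.
- If reduced disparity is claimed, also report risk differences by race/ethnicity group with confidence intervals.
- State which subgroups are key and which outcomes the race/ethnicity analysis covers.
- Label as post hoc any of these analyses that was not prespecified, since the document describes analyses already carried out.

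If an interaction model was in fact fitted, a sentence saying so and the resulting estimates are enough for that part.

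The cost is wording and a few lines of code on data already held. The downside is that interaction estimates are imprecise in small groups, so some apparent differences will not be claimable, and a non-significant interaction test will not by itself establish that effects are alike.

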Eligible patients were randomized into (2) arms: 1) an intervention arm and 2) a usual care arm. Those randomized to the intervention arm, at all sites, received encouragement to use existing mail order pharmacy services by receiving an outreach letter, which includes information about the benefits of mail order pharmacy use, and information on how to enroll in mail order pharmacy services at their individual site. The instructions on how to enroll in the existing mail order pharmacy services came directly from health plan operations materials. In addition, those randomized to the encouragement arm at KPNC and KPHI also received an encouragement outreach email (secure message) and pre-recorded phone message. Since phone and email contact with patients is not standard of care with HPHC, they received letter-only encouragement outreach. The letter and email outreach will be delivered only once. The Interactive Voice Response (IVR) system was programmed to make up to the IRB approved maximum attempts to contact eligible participants via phone to play the approved pre-recorded message: If a call is answered, the message begins. No PHI was disclosed in the outbound message. At the end of the call patients were given the opportunity to be transferred to their local mail order pharmacy phone line. Eligible members can hang up at any time and were not re-dialed. Those patients randomized to the usual care arm did not receive any outreach from the study team.

DATA ANALYSIS:

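### Primary care visits and hospitalisation/ED use are compared without prior-year utilisation, and the Kruskal-Wallis test gives no difference in visit volume; add an adjusted robust Poisson analysis beside it.

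*Combined protocol and SAP*

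**What the plan says.** The Data Analysis section names two comparisons of health-care use. For admissions and emergency care: "We used Chi-square tests to compare the percent of patients with a hospitalization or emergency department visit during follow-up". For primary care, the investigators "compared the number of primary care visits between arms using the Kruskal-Wallis test". It gives no effect measure, interval or baseline covariate for either. The only further step is by site ("All analyses were further stratified by site"), with the two KP sites then pooled.

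The same section uses modified Poisson regression, that is Poisson regression with robust variance, for risk ratios by race/ethnicity. It compares the share of fills sent by mail on the mean scale, with a t-test.

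Under Study Population, one entry criterion is "Have active health plan membership in the past 12 months". Non-adherence and the excluded diagnoses are also assessed over the preceding 12 months. The size is given as "63,012 total participants". The documents give no allocation ratio, significance level, power statement, site sizes or visit distribution. The two aims under Objective cover mail order use and adherence; health-care use appears in neither.

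**The concern.** There are two separate issues.

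1. **Unused baseline information.** A patient's visits in one year usually predict visits in the next. The plan records had to reach back 12 months to establish eligibility, so earlier visits, admissions and ED attendances should be available from them. A two-group Kruskal-Wallis test has no place for a covariate, and the chi-square test as specified has none either. Precision that would cost little to gain is left unused.

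2. **What the rank test reports.** With two arms, Kruskal-Wallis is the Wilcoxon rank-sum test. It asks whether counts in one arm tend to be higher than in the other. It does not say how many visits were added or saved. A patient who moves from 10 to 13 visits adds three to the total and hardly changes rank.

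At stake is how a null result is read. A reader could take a non-significant p-value as evidence that encouraging mail order left the volume of primary care unchanged, which this test alone cannot show.

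**Working it through.** The plan has no power or sample-size figure for these outcomes to reproduce. Only the total of 63,012 comes from the documents. The allocation ratio (1:1), two-sided 5% level, visit distributions, correlations and effect sizes below are assumptions.

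**Step 1: gain from adjusting the visit comparison.** In a randomised comparison, adjusting for a baseline value with correlation r to the outcome leaves approximately (1 − r²) of the variance.

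| r (assumed) | r² = variance saved | remaining variance |
|---|---|---|
| 0.33 | 0.11 | 0.89 |
| 0.48 | 0.23 | 0.77 |
| 0.63 | 0.40 | 0.60 |

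Simulated gamma-Poisson counts with mean 3 and shape 1.2 have variance 3 + 3²/1.2 = 10.5, so SD about 3.2. At these three correlations they gave adjusted-to-unadjusted variance ratios of 0.89, 0.77 and 0.60, which agrees with the formula.

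**Step 2: the same gain in visits.** Take all 63,012 patients at 1:1 (31,506 per arm) and an assumed SD of 4. The difference detectable with 80% power is (1.960 + 0.842) × SD × √(2/n) × √(1 − r²).
- r = 0: 2.802 × 4 × √(2/31,506) = 0.089 visits.
- r = 0.5: 0.0893 × √0.75 = 0.077.
- r = 0.7: 0.0893 × √0.51 = 0.064.

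The analysed number will be below 63,012: "Patients who died or who disenrolled from their health plan during follow-up were excluded from the analysis", and "those who did not have a CVD medication fill during the follow-up period were also excluded". This raises all three figures by the same factor.

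**Step 3: hospitalisation/ED.** The same formula with assumed correlations of 0.2 and 0.4 between prior-year and follow-up indicators gives 0.2² = 4% and 0.4² = 16%.

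**Step 4: does adjustment help in practice?** For a uniform 7% rise at 1,500 per arm, one simulation gave power of 39% for means unadjusted and 49% adjusted. Across the correlations in Step 1 the range was 37–43% unadjusted and 46–60% adjusted. Adjustment also raised power on the rank scale in the non-null scenarios examined. With no effect, rejection rates for all methods were close to 5%.

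**Step 5: ranks or means?** Power without adjustment, with ranges over repeated simulations:

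| Assumed effect | Per arm | Kruskal-Wallis | Means |
|---|---|---|---|
| 25% more visits, top tenth of attenders only | 5,000 | 6–11% | 86–90% |
| 25% more visits, lower half of attenders only | 1,500 | 46–52% | 19–23% |
| Uniform 7% rise, heavy-tailed counts | 1,500 | 26–34% | 18–26% |
| Uniform 2% fall, SD about 4.85 | 31,506 | 49% | 53% |

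Neither scale dominates. The ordering reverses with the place of the effect and the weight of the tail. The sizes of 1,500 and 5,000 per arm are illustrative, not site sizes taken from the documents.

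**The case against.** The best defence is that a rank comparison is a standard, valid choice for a skewed count. No section makes mean visits the target, and these outcomes lie outside both aims. That stands.

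A reader might infer something stronger: that Kruskal-Wallis is the wrong test, that it makes the trial blind to real changes in use, and that a comparison of means should replace it. The documents do not support this. The first row of the Step 5 table favours means strongly, but the next two favour ranks, and nothing in the documents says where an effect on visits would fall. Robust variance protects the validity of a mean comparison under extreme counts; it does not restore the power lost to them.

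Dilution also counts against the larger simulated effects. The intervention is one letter, plus a message and a recorded call at the KP sites. If encouragement raised mail order use by 5 to 20 percentage points (assumed) and acted on visits only through switching, a 25% rise at arm level would require a rise among switchers of 0.25/0.20 = 125% to 0.25/0.05 = 500%. With a 25% rise among top-tenth switchers and 10-point uptake, power at 31,506 per arm is about 7% for Kruskal-Wallis and 13% for means. The scenarios therefore compare methods; they do not forecast this trial.

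It can also be said that the savings rest on assumed correlations, that extraction of prior-year counts is unconfirmed, and that chi-square is appropriate for a randomised binary outcome. All three are true. They limit the size of the point, but they give no reason to ignore a baseline measure that is probably available.

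**Conclusion.** The point holds as one of efficiency and interpretation, not of validity. Both utilisation comparisons leave out prior-year use. The likely saving is about 11–40% of the variance for visits and 4–16% for hospitalisation/ED, given the correlations assumed above and provided that prior-year counts can be drawn from the plan records.

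The Kruskal-Wallis result is sound as a comparison of ranks but gives no visit volume. A non-significant p-value should not be reported as no change in mean visits. The case for adding a mean-scale estimate is that it answers how much care was used, not that it is always more sensitive. Importance is modest, because these outcomes are outside the stated aims.

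**What to change.** In the Data Analysis section, beside the existing tests:

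- **Visits:** add a Poisson model with robust variance, including arm and log(1 + visits in the 12 months before randomisation). Report the ratio and the difference in mean visits between arms with 95% confidence intervals, obtaining the difference by averaging predicted counts under each arm. Keep Kruskal-Wallis alongside.
- **Hospitalisation/ED:** fit the same model to the binary outcome, adjusted for prior-year hospitalisation/ED use, and report the risk ratio and risk difference.
- **Reporting:** state that a non-significant rank test does not show equal mean use, and state whether prior-year utilisation was extracted at all three sites.

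The section is written in the past tense. If the analyses are complete, label the additions as supplementary.

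The cost is a short addition to the plan and one further pull of pre-randomisation encounter data; no new participants or contacts are needed. The drawback is that the mean-scale estimate loses precision if a few patients have very high counts, which is a reason to keep the rank test beside it.

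### As written, the death, disenrolment and no-fill exclusions also reach the hospitalisation/ED and primary-care comparisons, where the no-fill reason does not fit and no stated analysis restores the patients who died or left the plan

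*Combined protocol and SAP*

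**What the plan says.** The DATA ANALYSIS section of the combined protocol and SAP goes through the comparisons in turn: mail order use and adherence (the only ones called intent-to-treat), share of fills by mail, risk ratios by race/ethnicity, and then utilisation. For utilisation it uses chi-square tests to "compare the percent of patients with a hospitalization or emergency department visit during follow-up between the intervention and control arm", and it "compared the number of primary care visits between arms using the Kruskal-Wallis test".

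The next sentence is "Patients who died or who disenrolled from their health plan during follow-up were excluded from the analysis". The one after adds that patients with no CVD fill during follow-up "were also excluded since we were unable to assess whether they used MOP". A single sensitivity analysis brings back the non-fillers by "including them in the analytic population as non-users of MOP at follow-up". The section gives no separate population for any outcome and no analysis that brings back patients who died or disenrolled.

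Elsewhere, STUDY POPULATION gives "63,012 total participants" without saying whether this is before or after exclusions. Aim 2 under OBJECTIVE asks whether "encouraging the use of mail order pharmacy services to deliver cardiometabolic medications results in greater medication adherence".

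**The concern.** Death, disenrolment and having no fill all arise after randomisation. Dropping patients on such conditions means the utilisation arms are no longer the arms that were randomised.

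The two rules raise different questions. For non-fillers, the stated reason concerns only whether mail order was used. An admission, an ED visit or a clinic visit can be recorded whether or not a prescription was filled. For deaths and disenrolments no reason is given. Incomplete records after leaving the plan would be a plausible reason for dropping disenrolled patients, but it does not explain discarding events recorded before death or departure.

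At stake is the between-arm difference in utilisation. Aim 2 itself tests whether outreach raises adherence, so whether a patient fills at all could depend on arm. If it does, and if the patients affected have a different admission risk, the comparison of retained patients can show a difference that outreach did not cause.

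**Working it through.** **Reading the text.** Both exclusions follow directly after the utilisation sentence and name no outcome. The sensitivity analysis restores only non-fillers, recoded on mail order use, and is not said to cover utilisation. Even if it were, deaths and disenrolments would stay out.

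**Inputs.** The documents give 63,012 participants and nothing else that can be used: no allocation ratio, follow-up length, event rate or exclusion count. There is no plan figure to reproduce. Everything below is illustration, with 1:1 allocation assumed (63,012 / 2 = 31,506 per arm) and no true effect on utilisation.

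1. *Level of the event percentage.* Dropping decedents lowers it by d × (h_d − h), where d is the share dying, h_d the event risk in decedents and h the risk in survivors. With d = 2–5%, h = 25–40% and h_d = 80–90%:
   - smallest: 0.02 × (0.80 − 0.40) = 0.8 points
   - largest: 0.05 × (0.90 − 0.25) = 3.25 points
   - central: 0.03 × (0.85 − 0.30) = 1.65 points, from 31.65% to 30.0%

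   If deaths are alike in both arms in number and type, and there is no true effect, the between-arm difference is not biased.

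2. *Deaths 3.0% (usual care) vs 2.5% (intervention), h = 30%, h_d = 85%.* The all-randomised risk is 31.65% in both arms.
   - Retained, usual care: 30.00%.
   - Retained, intervention: (0.97 × 0.30 + 0.005 × 0.85) / 0.975 = 30.28%.
   - False difference: 0.28 points.
   - SE = √[0.3028 × 0.6972 / (31,506 × 0.975) + 0.30 × 0.70 / (31,506 × 0.97)] = 0.37 points.
   - Ratio 0.76; chance of p < 0.05 about 0.12.

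3. *No fill 10% vs 8%.* Let h_m be the risk in patients who fill only because of outreach; other fillers have 30%. The difference is (0.90 × 0.30 + 0.02 × h_m) / 0.92 − 0.30.
   - h_m = 20%, 30%, 40% gives −0.22, 0 and +0.22 points.
   - SE 0.38 points; largest ratio 0.57; chance of p < 0.05 about 0.09.

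4. *Arm differences needed for a bias of one SE, same inputs.* Deaths: 0.66 points (3.0% vs 2.34%). No fill: about 3.6 points (10% vs 6.4%). With 1:2 or 1:3 allocation the SEs rise to 0.39–0.44 points, so cases 2 and 3 stay below one SE.

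5. *A harsher set of inputs.* Overall risk p = 20%, excluded share e, risk q in the excluded; retained risk = (p − e × q) / (1 − e). With e = 20% vs 18% and q = 40%: (0.20 − 0.08) / 0.80 = 15.0% against (0.20 − 0.072) / 0.82 = 15.6%, a false difference of 0.61 points. The SE is 0.32, so this is 1.9 SE, with a chance of p < 0.05 of about 0.48. With q = 10% instead, the difference is −0.31 points.

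6. *What a crude remedy would cost.* Suppose disenrolled patients are put back and counted only up to departure in a simple proportion. With 30% full-window risk, a constant event rate and half the window observed, the observed risk is 1 − √0.70 = 16.3%, a shortfall of 13.7 points. Each 1-point arm difference in disenrolment then adds about 0.14 points of error; at 6% vs 4% it adds 2 × 0.137 = 0.27 points, about the size of case 2.

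**The case against.** The strongest reply concerns scope. The section calls the comparison of mail order use and adherence an intent-to-treat analysis, and the exclusion sentence may refer back to that one. The no-fill reason, and the recoding of non-fillers as mail order non-users, both point to the mail order outcomes. This is plausible, and if it is what was meant, the no-fill part is a gap in wording only. The text does not say so, however, and it leaves the utilisation population undefined.

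The second reply is that the harm is hypothetical. The letter and email were sent once, and the STUDY DESIGN section says "There was no outreach follow-up". Deaths of 3.0% vs 2.5% would be a gap of about 3.8 SE of the death-rate difference (0.5 / 0.13), which chance would rarely produce and which such brief outreach is not expected to cause. The harsher case in step 5 combines high exclusion, a 2-point arm gap and doubled risk in the excluded, all assumed. This reply stands.

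The third is that adding disenrolled patients with shortened follow-up to a simple proportion brings in error that exclusion would avoid if disenrolment is non-informative. Raw visit counts have the same weakness. This also stands and shapes the fix.

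A reader might go further and infer that the utilisation results are biased, or that the primary result is undermined. The documents support neither. They give no exclusion counts by arm, and this point concerns utilisation only.

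**Conclusion.** The point holds in a limited form. As written, the three exclusions cover every comparison, the no-fill reason does not fit utilisation, and on any reading that applies the death and disenrolment rule to utilisation, no stated analysis restores those patients.

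Bias in the between-arm difference requires exclusions that differ by arm in number or type. If there is a true effect, the retained patients' effect may also differ from the effect in all randomised patients, even with equal exclusions. No bias is demonstrated. The two milder illustrations fall below one SE. Only stronger assumptions go beyond that, and neither the size nor the direction in this trial can be determined without counts by arm. Utilisation is in neither Aim, and the primary outcome is not affected by this point. It is worth considering, not a major defect; confidence is medium because the intended scope of the exclusions is unclear.

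**What to change.** 1. State the analysis population for each outcome, and do not apply the no-fill exclusion to utilisation.
2. Add a utilisation analysis of all randomised patients, from randomisation to the earliest of death, disenrolment or end of follow-up. Use cumulative incidence of hospitalisation/ED with death as a competing event and censoring at disenrolment, and primary-care visits per person-time. A simple proportion or raw count over shortened follow-up is not adequate, for the reason in step 6 of the working.
3. Report deaths, disenrolments and no-fill patients by arm. These counts alone would show whether the exclusions could have mattered.
4. Keep the existing chi-square and Kruskal-Wallis comparisons. The section is in the past tense and says the two KP sites were pooled partly because their results were similar, so results had been seen. The new analysis should be labelled as added afterwards, not silently substituted for the stated one.

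The cost is revised wording and one added analysis. Utilisation records for the excluded patients may need to be extracted, since the documents do not say that they were. Censoring at disenrolment assumes that leaving the plan is non-informative, which should be stated.
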